### **8.3. Use of Data from Early Discontinuation Cases**

Study data collected previously for patients who are discontinued from the study by the Investigator or lost to follow-up may still be included and used for the study unless the patient presents written notification of withdrawal of consent to the Investigator. In the event that a

#### **THINK Surgical, Inc.**

Proprietary rights of THINK Surgical, Inc. are involved in the subject matter of this material. It is submitted in confidence for a specific purpose and the recipient by accepting this material agrees that it will not be used other than for the express purpose for which it was delivered.

Disclosure to others without written permission from THINK Surgical, Inc. is forbidden.

patient withdraws consent to participate in the study, data previously collected for the patient may not be included or used for the study.

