
Statistical Methodology
	
Demographic, baseline, peri-operative and postoperative characteristics for all recruited cases will be assessed from data which is collected on the relevant case report forms. Continuous variables included in demographic, baseline, peri-operative and postoperative summaries, will be evaluated using descriptive statistics (N, mean, median, standard deviation, minimum, and maximum). Dichotomous and polychotomous variables included in demographic, baseline, peri-operative and postoperative summaries, will be described as frequencies and percentages at each level of the categorical variable.
 
The primary effectiveness and safety hypotheses will be tested using exact tests for a single proportion with one-sided type 1 error rate set to <math>\alpha=0.05</math>. The study success criterion requires rejection of both the effectiveness and safety null hypotheses.
 
The primary effectiveness endpoint, the safety endpoint and all secondary endpoints including bleeding and the individual components of the composite safety endpoint, will each be summarized by counts, percentages, and the upper bounds of one-sided 95% exact binomial confidence intervals (CI). Patient function and health related quality-of-life will be described by summarizing baseline, 3-month, 6 month, 12 month (if available) and change scores at each time point in the Knee Society Scores and SF-12 Health Survey Physical and Mental Health Composite Scores (PCS & MCS), using descriptive statistics including mean, standard deviation, median, minimum, and maximum. The ITT analysis set will be used in primary analyses. Specific analyses may be repeated in a Per Protocol analysis set that requires completion of the index procedure and no clinically significant protocol violations.
 
Continued Access Study Arm
 
The continued access study arm will not include any hypothesis testing and will not be part of the primary or secondary endpoint analysis. Data from the continued access arm will be provided as descriptive statistics, which can include counts, percentages, mean, standard deviation, median, minimum, and maximum and the upper bounds of one-sided 95% exact binomial confidence intervals (CI). This will include an analysis of safety, patient function, and health related quality-of-life data described by summarizing baseline, 6 week, 3-month, 6 month, 12 month (if available) and change scores at each time point, as applicable.

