#### 5.1. Primary Effectiveness Endpoint

The primary effectiveness endpoint is alignment of coronal mechanical axis at 3 months defined as achieving varus-valgus alignment less than or equal to  $\pm 3^\circ$  in the frontal plane after TKA compared to the pre-operative plan. A review of 1,376 patients undergoing conventional TKA with manual instrumentation showed a 32% malalignment for mechanical axis greater than 3° (Mason). This

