## 6.5. Study Enrollment

Each Investigator shall maintain a Screening & Enrollment Log for all primary TKA patients that are recruited for the clinical trial and screened for eligibility. This log will be used to document all patients who agree to be screened, including the ones that withdraw consent during the screening process or are determined not to meet the eligibility criteria. If a patient is excluded from the study, the reason for exclusion will be recorded on the log. Patients who meet the eligibility criteria and consent to participate shall be assigned a unique Subject Identification Number that will be captured on the Screening & Enrollment Log and used to identify them on all source documents and Case Report Forms thereafter. Patients will be considered to be enrolled once they have signed the Informed Consent Form and been assigned a Subject Identification Number. Enrolled patients that elect to withdraw consent prior to treatment with the investigational device will be considered screen failures under inclusion criteria (e).

Patients who do not meet eligibility criteria will have the primary reason for ineligibility captured in the study database on the Eligibility Criteria eCRF. No other CRFs will be completed for these patients.

Once enrollment is complete in the IDE Study Arm, subjects will be enrolled into the Continued Access Arm.

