#### **THINK Surgical, Inc.**

Proprietary rights of THINK Surgical, Inc. are involved in the subject matter of this material. It is submitted in confidence for a specific purpose and the recipient by accepting this material agrees that it will not be used other than for the express purpose for which it was delivered.

Disclosure to others without written permission from THINK Surgical, Inc. is forbidden.

Table 2 – Schedule of Procedures (IDE Study Arm)

	Baseline Visit a	Surgical Visit	Hospital Discharge	6 Weeks (± 2 weeks)	3 Months (± 2 weeks) Primary Endpoint	6 Months (± 2 weeks)	12 Months (± 2 weeks)
Informed Consent	X						
Inclusion/Exclusion Criteria	X						
Demographics	X						
Medical History & Physical Exam	X						
TPLAN Operative Planning	X						
TCAT-Assisted TKA (Investigational Procedure)		X					
Hemoglobin and Hematocrit Assessment		X b	X b				
Transfusion Summary			X b				
Standing long-leg X-rays	X AP, WB				X AP, WB	X AP, WB	
Standard X-ray	X L,NWB	X AP/L, NWB*		X AP,WB & L,NWB	X L,NWB	X L,NWB	X AP,WB & L,NWB
3D CT Imaging	X a				X		
Knee Society Score (KSS) Survey	X			X	X	X	X
SF-12 Health Survey	X			X	X	X	X
Concomitant Medications/Therapies	X	X	X	X	X	X	X
Safety Evaluation c		X	X	X	X	X	X
Study Completion d						X d	X d

AP = Anteroposterior View, L = Lateral View, WB = weight bearing, NWB = non-weight bearing

- Baseline Visit procedures may be completed in >1 clinic visit if required, but must be completed within 90 days prior to the date of surgery. The preoperative CT scan for surgical planning must be taken within 30 days prior to the date of surgery.
- Patients will have their hemoglobin and hematocrit levels measured preoperatively no earlier than 30 days prior to the surgical procedure and postoperatively no more than 3 days after the procedure. Patients who are discharged on the date of surgery will have their postoperative hemoglobin and hematocrit levels measured and their transfusion summary documented on Day 0 prior to discharge.
- Patients with ongoing adverse events at their last study visit will be followed until the adverse event is resolved, no further improvement is expected, or the patient has completed study participation and is exited from the study.

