**The total sample size to be enrolled is equal to 115 (103 plus 10% for possible loss-to-follow-up).**

It can be noted that with N=103, the number (%) of patients experiencing the primary composite safety event must be no larger than 8 (7.8%) in order to achieve the primary study success criterion. With 8 of 103 patients experiencing the event, the upper bound of the one-sided 95% exact binomial confidence interval will be 0.1358 which is less than 0.136, thereby permitting rejection of the inferiority hypothesis and a conclusion of no clinically significant increase in the incidence of the composite safety endpoint.

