#### IDE Study Arm

The primary effectiveness endpoint, the safety endpoint and all secondary endpoints including bleeding and the individual components of the composite safety endpoint, will each be summarized by counts, percentages, and the upper bounds of one-sided 95% exact binomial confidence intervals (CI).

Patient function and health-related quality-of-life will be similarly addressed by summarizing baseline, 6-week, 3-month, 6-month, and 12-month (if available) reported outcomes and change at each time point in the Knee Society Scores and SF-12 Health Survey Physical and Mental Health Composite Scores (PCS & MCS), using descriptive statistics including mean, standard deviation, median, minimum, and maximum. The ITT analysis set will be used in all safety analysis. Specific analyses may be repeated in a Per Protocol analysis set that requires completion of the index procedure and no clinically significant protocol violations.

Intraoperative and immediate postoperative complication rates will be similarly summarized using descriptive statistics.

In addition to the above analyses, key safety and effectiveness results will be stratified by certain baseline characteristics (investigational site, age, gender, and median value of Knee Society Score) to confirm that the safety and efficacy of the TSolution One™ Surgical System is consistent among different subgroups.

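### Section 8.3 bars every item of data from a treated patient who withdraws consent, including recorded composite safety events; this does not fit the ITT set, and its effect on the safety test depends on withdrawal rates the plan does not give

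*Combined protocol and SAP*

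**What the plan says.** Section 8.3 has two sentences on patients who leave early. The first is permissive: "Study data collected previously for patients who are discontinued from the study by the Investigator or lost to follow-up may still be included", unless the patient gives written notice of withdrawing consent. The second is a bar: where a "patient withdraws consent to participate in the study, data previously collected for the patient may not be included or used for the study". The second sentence has no written-notice condition and no exception for treated patients or recorded safety events.

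Section 6.5 deals separately with withdrawal before surgery: "Enrolled patients that elect to withdraw consent prior to treatment with the investigational device will be considered screen failures".

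On the analysis set, the Statistical Methodology part of Section 1 says "The ITT analysis set will be used in primary analyses", and Section 9.3 says "The ITT analysis set will be used in all safety analysis". Neither defines ITT or refers to 8.3, and there is no missing-data rule or sensitivity analysis for the primary tests.

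The only attrition figure is in 9.1: 115 patients, being 103 plus 10% for loss to follow-up. No rate of consent withdrawal is given, overall or by event status.

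**The concern.** Because 6.5 already removes those who withdraw before treatment, the bar in 8.3 bites in the primary analyses on patients who have had the procedure. Some may already have a composite event on record. Their removal follows from a decision taken after treatment, possibly because of how the treatment went. An ITT set, as the term is normally used, is meant to prevent that.

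This is a single-arm trial judged by a count of events against a fixed rate, so there is no control arm in which the same loss might partly cancel. If patients with events withdraw consent more often than the others, the observed rate is biased downwards and the safety test can pass too easily. If both groups withdraw alike, the rate is unbiased but patients and power are lost.

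**Working it through.** **Inputs.** From Section 1 and 9.1: null rate 0.076 + 0.06 = 0.136; planning rate 0.0608; one-sided exact binomial test at 0.05; N=103 evaluable, 115 enrolled. (Section 5.2 prints a margin of 7.0%. That is a separate matter; the plan's power figure reproduces with 0.06, which is used here.) Assumed, because the documents give nothing: wE and wN, the probabilities that a treated patient with or without an event withdraws consent.

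**1. The plan's own figures.** The cutoff c is the largest count with P(X ≤ c | n, 0.136) ≤ 0.05.

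- n=103: c=8, P(X ≤ 8 | 0.136) = 0.0494, upper one-sided 95% bound 0.1358, power P(X ≤ 8 | 0.0608) = 0.8252. The plan states 8, 0.1358 and 82.5%.
- n=115: c=9, alpha 0.0404, power 0.8378. The plan states 83.7%.

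**2. One trial at the boundary.**

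- 10/115: p=0.075, fail. Remove one event patient: 9/114, p=0.043, pass.
- 9/103: p=0.092, fail. Remove one: 8/102, p=0.053, still a fail. Remove two: 7/101, p=0.028, pass.

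One removal can therefore be enough at 115, while two are needed at 103.

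**3. Alpha under the deletion rule.** With true rate p, the share removed is q = p·wE + (1−p)·wN. The event rate among those kept is p′ = p(1−wE)/(1−q). The rejection probability is the sum over m of P(m kept | N, 1−q) × P(X ≤ c_m | m, p′), with the cutoff c_m reset at each m. Setting p=0.136 gives alpha; p=0.0608 gives power.

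Example, 10/0%: q = 0.136 × 0.10 = 0.0136; p′ = 0.136 × 0.90 / 0.9864 = 0.1241.

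| wE / wN (assumed) | Expected removals at N=115, 115·q (p=0.136) | Alpha, N=115 | Alpha, N=103 |
|---|---|---|---|
| 0 / 0% | 0 | 0.040 | 0.049 |
| 5 / 5% | 5.75 | 0.033 | 0.035 |
| 10 / 10% | 11.5 | 0.037 | 0.035 |
| 5 / 10% | 10.7 | 0.025 | 0.024 |
| 10 / 5% | 6.5 | 0.0495 | 0.052 |
| 5 / 0% | 0.8 | 0.060 | 0.053 |
| 10 / 0% | 1.6 | 0.082 | 0.066 |

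Power at N=115 is 83.8% with no withdrawal, 78.6% at 5/5% and 78.1% at 10/10%. The 10/10% case uses up the plan's whole loss allowance, so it is a high one.

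At N=115 with wN=0, alpha first exceeds 0.05 at wE of about 2.6%. That is 115 × 0.136 × 0.026 = 0.4 expected withdrawals. Low overall withdrawal is therefore no safeguard by itself; the difference between the groups is what counts.

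**4. What keeping recorded events achieves.** Let g be the share of withdrawing patients' events recorded before they withdraw (assumed). Take 10/0% at N=115.

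- g=1: no event is lost, alpha 0.040.
- g=0.5: half of the 10% are still lost. If those patients are left out, this is the 5/0% case, alpha 0.060. If they are counted as non-events, the rate is 0.136 × 0.95 = 0.1292 at n=115, alpha 0.061.
- g=0, left out: nothing changes, alpha 0.082.

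**5. Tipping-point illustration.** Suppose 115 are treated, 3 withdraw, and there are 8 events in the 112 kept: p=0.025, pass. With all 115 in the denominator and 0, 1, 2 or 3 of the three counted as events, p = 0.020, 0.040, 0.075 or 0.128. The conclusion changes at two.

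**The case against.** The strongest reply has four parts.

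- *ITT is undefined.* The conflict is with the customary meaning, not with a stated definition. This stands, and it limits the wording of the point. It does not remove it, since no passage reconciles 8.3 with the set that Sections 1 and 9.3 name.
- *The text is ambiguous rather than a clear bar.* Section 8.1 lists consent withdrawal among the reasons for investigator discontinuation, 8.2 asks only that sites try to get it in writing, and the first sentence of 8.3 keeps data absent written notice. That reading is possible, but the second sentence of 8.3 is unqualified and points the other way. Whether an event counts should not turn on how a departure was documented.
- *The rule may mirror a promise in the consent form.* The form is not available for this review, so this cannot be excluded. Any remedy must stop where the signed consent stops.
- *Keeping the data does not cure the bias.* This is right: at 10/0% with half the events recorded first, alpha is still about 0.060.

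A tempting companion rule would drop event-free leavers from the safety denominator while keeping leavers with events. That would make exclusion depend on outcome and would reach patients whose data 8.3 now allows to be used. It is not proposed here.

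**Conclusion.** The point holds as an inconsistency that should be fixed. A stated rule can remove a recorded, deciding safety event from a treated patient, and it does not fit the analysis set the plan names.

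A reader might go further and infer that 8.3 inflates the type 1 error rate. The documents do not support that. Inflation needs event patients to withdraw sufficiently more often than the others. Equal withdrawal leaves alpha below 0.05 and costs about 5 to 6 points of power at 5% or 10%, and the reverse pattern lowers alpha. No withdrawal rates are given, so neither size nor direction is established, and every alpha under withdrawal above rests on assumed rates. A reader might equally infer that rare withdrawal makes the rule harmless; the break-even of 2.6% against 0% shows that this does not follow either.

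The rule does not reach patients lost to follow-up or discontinued by the investigator for other reasons. How event-free leavers are handled, the length of the safety window and the handling of missing 3-month radiographs are separate matters, to be stated in advance whatever becomes of 8.3.

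**What to change.** 1. In 8.3, delete the 'unless' clause of the first sentence and replace the second, for both arms, with: *If a treated patient withdraws consent, no further data are collected. Data collected up to withdrawal are kept and used to the extent the signed consent permits. In the IDE Study Arm, any composite safety event recorded before withdrawal counts as an event in the primary safety analysis.* This also ends the mismatch within 8.3 between written and unwritten withdrawal.
2. Report the number of consent withdrawals after treatment.
3. As a sensitivity analysis only, give a tipping-point table for the primary safety test. It counts from none to all of the patients with unusable or incomplete safety data as events, with all treated patients in the denominator.

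The cost is protocol wording, one table, and possibly a slightly less favourable observed event rate. Item 1 removes the bias only if every event of a withdrawing patient was recorded before withdrawal; otherwise it reduces it, and item 3 shows how far the conclusion depends on the rest. Where the signed consent promised removal of data, only items 2 and 3 apply.

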#### 8.4. Treatment for Early Discontinuation Cases

Patients who withdraw voluntarily or are discontinued by the Investigator will remain eligible for Standard of Care treatment by the Investigator and study staff.

#### 8.5. Stopping Rules

The Sponsor reserves the right to stop the study at any time in the event that there is a device-related serious adverse event or unanticipated adverse device effect which the Sponsor believes signals a safety concern for study participants. The Sponsor also reserves the right to stop the study for non-safety related issues, including but not limited to usability failures.

Refer to Section 10.7 (Study Termination) for additional details regarding study termination procedures for any event that leads the sponsor to believe the investigational device presents an unreasonable risk to study patients.

### 9. STATISTICAL PLAN

#### 9.1. Determination of Sample Size for Safety Endpoint

##### IDE Study Arm

The primary safety hypothesis for this study is that the probability of experiencing the composite safety endpoint for patients undergoing TCAT-assisted implantation using the TSolution One System for TKA is not clinically significantly elevated relative to the historic control value of 7.6% for manual TKA. Symbolically, the primary safety hypotheses regarding non-inferiority relative to historical control may be represented as follows:

**$H_0: \pi_i \geq \pi_c + \delta$  (clinically inferior safety)**

**$H_A: \pi_i < \pi_c + \delta$  (not clinically inferior safety)**

In this formulation,  $\pi_i$  and  $\pi_c$  are the true event rates when using the investigational device and manual TKA, respectively. As noted above, based on a literature review,  $\pi_c = 0.076$ . A non-inferiority margin of 0.06 was selected. Therefore, these hypotheses reduce to:

**$H_0: \pi_{\text{composite}} \geq 0.076 + 0.06 = 0.136$**

**$H_A: \pi_{\text{composite}} < 0.076 + 0.06 = 0.136$**

A one-sided Fisher's exact test will be used to test the primary safety hypothesis that the composite safety event rate is larger than historical control (0.076) plus the non-inferiority margin of  $\delta=0.06$ . That is, the null hypothesis is that the investigational device event rate is 0.136 or larger and the alternative hypothesis is that this event is less than 0.136. Based on the Sponsor's expectation that the technology is associated with improved outcomes, it was assumed for the purpose of sample size determination that that composite safety event rate for patients undergoing primary TKA with femoral and tibial preparation by the TSolution One™ Surgical System is 20% smaller than control, or equal to 0.0608. A one-sided type 1 error of  $\alpha=0.05$  was

#### THINK Surgical, Inc.

Proprietary rights of THINK Surgical, Inc. are involved in the subject matter of this material. It is submitted in confidence for a specific purpose and the recipient by accepting this material agrees that it will not be used other than for the express purpose for which it was delivered.

Disclosure to others without written permission from THINK Surgical, Inc. is forbidden.

assumed. Using industry standard software (nQuery Advisor 7.0, Module POT0x-1), it was determined that statistical power to reject the non-inferiority hypothesis was equal to 82.5% with a sample size of N=103. Because of the discreteness of the exact binomial distribution, the power curve is not monotonic. Power for sample sizes of N=102, 103, 104, 105, 106, 107, 108, 109, 110, 111, 112, 113, 114, 115, 116, 117, 118, 119, 120, 121 and 122 are 71.9%, 82.5%, 81.8%, 81.1%, 80.3%, 79.6%, 78.9%, 78.1%, 77.3%, 76.6%, 75.8%, 84.9%, 84.3%, 83.7%, 83.1%, 82.5%, 81.8%, 81.1%, 80.5%, 79.8%, and 87.6%. The smallest sample size with power  $\geq 80\%$  is 103. For sample sizes of N=103 and above, power never falls below 75.8%. The minimum sample size for which power remains at least equal to 80% at that value for all larger values is N=113.

**The total sample size to be enrolled is equal to 115 (103 plus 10% for possible loss-to-follow-up).**

It can be noted that with N=103, the number (%) of patients experiencing the primary composite safety event must be no larger than 8 (7.8%) in order to achieve the primary study success criterion. With 8 of 103 patients experiencing the event, the upper bound of the one-sided 95% exact binomial confidence interval will be 0.1358 which is less than 0.136, thereby permitting rejection of the inferiority hypothesis and a conclusion of no clinically significant increase in the incidence of the composite safety endpoint.

#### Continued Access Arm

There will be no formal hypothesis testing for the Continued Access Arm of the study. Patients will be followed for safety and to gain additional information on device use, therefore, no power analysis has been performed to estimate sample size. The Continued Access Arm will enroll up to 50 patients.

## 9.2. Determination of Sample Size for Effectiveness Endpoint

### IDE Study Arm

A review of 1,376 patients undergoing conventional TKA showed a 32% malalignment for mechanical axis greater than 3° (13). This proportion will be used as the comparative constant proportion for 3-month follow-up for conventional TKA in this study.

The primary effectiveness hypothesis for this study is that the probability of malalignment for patients undergoing TCAT-assisted implantation using the TSolution One System for TKA is 50% smaller than the reference rate of 32%, that is, 16%.

